10.0 LABELING, PACKAGING, STORAGE, AND RETURN OF CLINICAL SUPPLIES

10.1 Intralesional IL-2

10.1.1 Formulation, Preparation, Packaging and Handling

Intralesional IL-2 (also referred to as Proleukin® or aldesleukin) is a sterile, white to off-white, preservative-free, lyophilized powder. IL-2 vials should be stored in a refrigerator at 2-8 °C, protected from light and stored in carton. Each vial contains 22 million international units (1.3 mg). Reconstitute each vial with 1.2 mL sterile water for injection (sWFI). Do not shake. Do not reconstitute with 0.9% NaCl or bacteriostatic water for injection. Resultant concentration is 18 million international units/mL (1.1 mg/mL). IL-2 may be further diluted in D5W for final concentration of 30-70 mcg/mL. Avoid bacteriostatic water for injection and NS for reconstitution or dilution.

10.1.2 Administration

The final diluted dose will be delivered to the treatment lesion through intralesional needle placement. Needle placement will be performed by palpation or using ultrasound or computed tomography guidance as indicated. 4 intralesional injections will be administered over a 2-week period with two treatments each week and individual treatments will be a minimum of 48 hours apart.

10.1.3 Disposal and Destruction

Drug supply will either be disposed of at the study site according to the study site's institutional standard operating procedure. Accurate records of all investigational product received at, dispensed from, returned to, and disposed of by the study site should be recorded on the drug accountability form.

10.1.4 Supplier

Intralesional IL-2 will be supplied by the study.

10.2 Pembrolizumab

The investigator shall take responsibility for and shall take all steps to maintain appropriate records and ensure appropriate supply, storage, handling, distribution and usage of investigational product in accordance with the protocol and any applicable laws and regulations. Table 15

Pembrolizumab (also referred to as Keytruda® and MK-3475) will be provided by Merck as summarized in Table 15. Table 15 Pembrolizumab will be administered using a dose of 200 mg Q3W.

Table 15. Pembrolizumab Drug Information

Product Name & Potency	Dosage Form
Pembrolizumab 100 mg/4mL (single use vial)	Solution for Injection

10.2.1 Packaging and Labeling Information

Clinical supplies will be affixed with a clinical label in accordance with regulatory requirements. For complete details on drug preparation, administration, storage conditions, clinical pharmacology, pharmacokinetics, and known precautions and adverse reactions please see the pembrolizumab IB and or the package insert.

10.2.2 Preparation and Administration

The solution should be visually inspected for particulate matter and discoloration prior to administration. Pembrolizumab solution is clear to slightly opalescent, colorless to slightly yellow. Discard the vial if visible particles are observed. Withdraw the required volume of pembrolizumab from the vial(s) of pembrolizumab and transfer to an intravenous (IV) bag containing 0.9% Sodium Chloride Injection, USP or 5% Dextrose Injection, USP. Mix diluted solution by gentle inversion. The final concentration of the diluted solution should be between 1 mg/mL to 10 mg/mL. Discard unused portion of the vial.

Administer pembrolizumab IV infusion over 30 minutes every 3 weeks through an intravenous line containing a sterile, non-pyrogenic, low-protein binding 0.2 micron to 5 micron in-line or add-on filter. Do not infuse other medications through the same infusion line.

10.2.3 Clinical Supplies Disclosure

This trial is open-label; therefore, the subject, the trial site personnel, the Sponsor-Investigator and/or designee are not blinded to treatment. Drug identity (name, strength) is included in the label text; random code/disclosure envelopes or lists are not provided.

10.2.4 Storage and Handling Requirements

Pembrolizumab vials must be stored in the refrigerator at 2° to 8°C (36°F to 46°F). Pembrolizumab injection solution should be stored in original carton to protect from light; do not freeze or shake vials.

The product does not contain a preservative, Pembrolizumab should be used immediately after preparation. Pembrolizumab solutions diluted for infusion in NS or D5W may be stored at room temperature for no more than 6 hours from the time of reconstitution or dilution. This includes room temperature storage of the reconstituted vials, storage of the infusion solution in the IV bag, and the duration of infusion. Alternatively, pembrolizumab infusion solutions may be stored under refrigeration at 2 to 8°C (36 to 46°F) for no more than 24 hours from the time reconstitution or dilution and protected from light. The infusion should not be frozen.

Clinical supplies must be stored in a secure, limited-access location under the storage conditions specified on the label. Receipt and dispensing of trial medication must be recorded by an authorized person at the trial site. Clinical supplies may not be used for any purpose other than that stated in the protocol.

10.2.5 Drug Disposal and Accountability

The investigator and the assigned pharmacist or designee are responsible for drug accountability. Drug supply will be disposed of according to institutional standard operating procedures and policies. Accurate records of all investigational product received at and dispensed from the study site should be recorded on the drug accountability record.

10.2.6 Supplier

Pembrolizumab will be supplied by the study.

11.0 ETHICAL CONSIDERATIONS AND ADMINISTRATIVE PROCEDURES

11.1 Ethics and Good Clinical Practice

This study must be carried out in compliance with the protocol and Good Clinical Practice, as described in:

1. International Council for Harmonisation (ICH) Harmonized Tripartite Guidelines for Good Clinical Practice 1996.
2. Directive 91/507/EEC, The Rules Governing Medicinal Products in the European Community.
3. US 21 Code of Federal Regulations dealing with clinical studies (including parts 50 and 56 concerning informed consent and IRB regulations).
4. Declaration of Helsinki, concerning medical research in humans (Recommendations Guiding Physicians in Biomedical Research Involving Human Subjects, Helsinki 1964, amended Tokyo 1975, Venice 1983, Hong Kong 1989, Somerset West 1996).

The investigator agrees, when signing the protocol, to adhere to the instructions and procedures described in it and thereby to adhere to the principles of Good Clinical Practice that it conforms to.

11.2 Institutional Review Board

The protocol, the proposed informed consent form, and all patient-facing documents must be reviewed and approved by a properly constituted Institutional Review Board before any research involving human subjects has been conducted. Prior to obtaining IRB approval, the protocol must be approved by the UC Davis Comprehensive Cancer Center Scientific Review Committee (SRC).

11.3 Informed Consent

The investigator must explain to each subject (or legally authorized representative) the nature of the study, its purpose, the procedures involved, the expected duration, the potential risks and benefits involved and any discomfort it may entail. Each subject must be informed that participation in the study is voluntary and that he/she may withdraw from the study at any time and that withdrawal of consent will not affect his/her subsequent medical treatment or relationship with the treating physician.

This informed consent should be given by means of a standard written statement, written in non-technical language. The subject should read and consider the statement before signing and dating it and should be given a copy of the signed document. If the subject cannot read or sign the documents, oral presentation may be made or signature given by the subject's legally appointed representative, if witnessed by a person not involved in the study, mentioning that the patient could not read or sign the documents. No patient can enter the study before his/her informed consent has been obtained.

The informed consent form is considered to be part of the protocol and must be submitted by the investigator with it for IRB approval.

11.4 Patient Confidentiality

In order to maintain patient privacy, all study reports and communications will identify the patient by initials and the assigned patient number. Medical records of patients will be maintained in strict confidence according to legal requirements. The patient's confidentiality will be maintained and will not be made publicly available to the extent permitted by the applicable laws and regulations.

11.5 Protocol Compliance and Deviations

The investigator will conduct the study in compliance with the protocol given approval/favorable opinion by the IRB and the appropriate regulatory authority(ies). Changes to the protocol will require approval from Merck and written IRB approval/favorable opinion prior to implementation, except when the modification is needed to eliminate an immediate hazard(s) to patients. The IRB may provide, if applicable regulatory authority(ies) permit, expedited review and approval/favorable opinion for minor change(s) in ongoing studies that have the approval /favorable opinion of the IRB. The investigator will submit all protocol modifications to Merck and the regulatory authority(ies) in accordance with the governing regulations.

All protocol deviations will be reported in accordance with UCD IRB Administration and UCD Cancer Center OCR policies and the participating site's IRB policies. Any departures from the protocol must be fully documented in the source documents.

11.6 Onsite Audits

Regulatory authorities or the IRB may request access to all source documents, data capture records, and other study documentation for on-site audit or inspection. Direct access to these documents must be guaranteed by the investigator, who must provide support at all times for these activities.

11.7 Premature Closure of the Study

This study may be prematurely terminated, if in the opinion of the investigator or Merck, there is sufficient reasonable cause. Written notification documenting the reason for study termination will be provided to the investigator or Merck by the terminating party.

11.8 Record Retention

The investigator will maintain all study records according to ICH-GCP and applicable regulatory requirement(s).

11.9 Quality Assurance

Quality assurance audits of select patients and source documents may be conducted by the Quality Assurance and/or Data Safety Committees as outlined in the UC Davis Cancer Center Data and Safety Monitoring plan. Quality control will be maintained by the OCR Quality Assurance team according to OCR policy.

12.0 OVERSIGHT AND MONITORING

12.1 Data and Safety Monitoring

In addition to the requirements for adverse event reporting as outlined in Section 7.3, this protocol is also subject to the UC Davis Comprehensive Cancer Center's (UCDCCC) Data and Safety Monitoring Plan. The UCDCCC is committed to pursuing high-quality patient-oriented clinical research and has established mechanisms to ensure both scientific rigor and patient safety in the conduct of clinical research studies. The UCDCCC relies on a multi-tiered committee system that reviews and monitors all cancer clinical trials and ensures the safety of its participants, in compliance with institutional and federal requirements on adverse event (AE) reporting, verification of data accuracy, and adherence to protocol eligibility requirements, treatment guidelines, and related matters. This trial has been assigned high risk level per the Data and Safety Monitoring Plan (DSMP) version July 1, 2020, Table 3 Risk Stratification of Trials, which defines the frequency at which this trial will be audited, monitored, and reviewed by the Data and Safety Monitoring Committee (DSMC) (see Appendix 6).

12.2 Investigator Monitoring Guidelines

Investigators will conduct continuous review of patient safety while on study treatment.

14.0 APPENDICES

Appendix 1: ECOG Performance Status Scale

Karnofsky Status	Karnofsky Grade**	ECOG Grade	ECOG Status**
Normal, no complaints	100	0	Fully active, able to carry on all pre-disease performance without restriction
Able to carry on normal activities. Minor signs or symptoms of disease	90	1	Restricted in physically strenuous activity but ambulatory and able to carry out work of a light or sedentary nature, e.g., light house work, office work
Normal activity with effort	80		
Care for self. Unable to carry on normal activity or to do active work	70	2	Ambulatory and capable of all selfcare but unable to carry out any work activities. Up and about more than 50% of waking hours
Requires occasional assistance, but able to care for most of his needs	60		
Requires considerable assistance and frequent medical care	50	3	Capable of only limited selfcare, confined to bed or chair more than 50% of waking hours
Disabled. Requires special care and assistance	40		
Severely disabled. Hospitalization indicated though death nonimminent	30	4	
Very sick. Hospitalization necessary. Active supportive treatment necessary	20		Completely disabled. Cannot carry on any selfcare. Totally confined to bed or chair
Moribund	10		
Dead	0	5	Dead

* KPS will be used in this study. ECOG status is listed for reference.

Appendix 2: Data Collection

All data will be collected using UC Davis data collection forms. Any and all source documentation shall be maintained.

Appendix 3: Molecular Correlative Sample Handling

Specimen Submission for Correlative Studies:

Patients must be offered participation in these molecular correlative studies. With the patient's consent, tissue and blood specimens will be submitted as outlined below. Samples will be de-identified and coded with a new patient ID number to protect patient's identity.

Specimen Collection, Storage, Shipping and Submission Requirements

It is required that paraffin-embedded tissue blocks or slides from time of diagnosis (or subsequent, but prior to therapy) as well as blood specimens, as outlined below, be submitted for expression of relevant molecular targets.

- **Archival tumor specimens:** If available, 1 - 2 paraffin-embedded tissue blocks containing formalin-fixed tumor or needle aspirate slides from time of diagnosis (or subsequent, but prior to therapy) should be submitted for evaluation of expression of PD-L1 and other relevant molecules. Paraffin blocks may be processed according to standard institutional protocols. If blocks are unavailable, 16 unstained slides are acceptable alternatives.
- **Fresh tumor biopsy:** **All specimens must be labeled with protocol number, patient registration number, and date of specimen collection.** Tissue portions will be used for (in order of priority):
 1. Fixed in formalin for the preparation of FFPE blocks
 2. Placed in 1 ml RNA later and snap frozen with liquid nitrogen and stored at -70 to -80°C for future RNA extraction and qPCR and immunochip analysis,
 3. Snap frozen with liquid nitrogen and stored at -70 to -80°C for future DNA extraction
- **Blood specimens:** Blood specimens (3 x 10 ml lavender top EDTA tubes) will be collected from each patient.

Each purple-top (EDTA) tube should be delivered to the lab where it will be inverted several times, and placed on wet ice until centrifugation. The tubes should be centrifuged as soon as possible at approximately 600 x g for 10 minutes. Approximately 1.5 ml of plasma should be removed from each tube and pooled in a fresh, sterile 15 ml conical tube. Centrifuge plasma a second time at 1500-1600 x g for 5 – 10 minutes to pellet and remaining cells. After the second spin, plasma should be removed and placed in 500 ul aliquots in labeled cryotubes. Plasma will be frozen and stored at -70 to -80°C. Plasma samples will be assayed by Luminex to evaluate systemic cytokine levels.

Blood remaining in the original EDTA tubes will be processed for PBMC collection. Briefly, blood cells will be resuspended in room temperature PBS at a 2:1 ratio. The blood will then be carefully layered over Lymphocyte Separation Media (Ficol Solution, LSM) and centrifuged at 400 x g for 30 minutes. Resulting cells will be washed twice in PBS then resuspended in RPMI to facilitate cell counting. To retain viability of cells,

cells will be frozen at about 1.0×10^7 in a freezing media consisting of 50% RPMI, 40% FBS, & 10% DMSO. Cells will be frozen at $-1^{\circ}\text{C}/\text{minute}$, the optimal rate for cell preservation. Cryopreserved cells will be stored in a liquid nitrogen freezer.

Appendix 4: Immune-Related Response Criteria (irRC)

Increasing clinical experience indicates that traditional response criteria (e.g., Response Evaluation Criteria in Solid Tumors, Version 1.1 [RECIST v1.1] and World Health Organization [WHO]) may not be sufficient to characterize fully activity in the new era of target therapies and/or biologics. In studies with cytokines, cancer vaccines, and monoclonal antibodies, complete response, partial response, or stable disease has been shown to occur after an increase in tumor burden as characterized by progressive disease by traditional response criteria.

Therefore, conventional response criteria may not adequately assess the activity of immunotherapeutic agents because progressive disease (by initial radiographic evaluation) does not necessarily reflect therapeutic failure. Long term effect on the target disease must also be captured. The immune related response criteria [60] (irRC) are criteria that attempt to do that by enhancing characterization of new response patterns that have been observed with immunotherapeutic agents (i.e., ipilimumab). (Note: The irRC only index and measurable new lesions are taken into account.)

GLOSSARY

Term	Definition
SPD	sum of the products of the two largest perpendicular diameters
Tumor burden	$SPD_{\text{index lesions}} + SPD_{\text{new, measurable lesions}}$
Nadir	minimally recorded tumor burden
irCR	immune-related complete response
irPD	immune-related progressive disease
irPR	immune-related partial response
irSD	immune-related stable disease
irBOR	immune-related best overall response

BASELINE ASSESSMENT USING irRC

Step 1. Identify the index lesions (five lesions per organ, up to ten visceral lesions and five cutaneous lesions).

Step 2. Calculate the SPD of all of these index lesions:

$$SPD = \sum_i (\text{Largest diameter of lesion } i) \times (\text{Second largest diameter of lesion } i).$$

POST-BASELINE ASSESSMENTS USING irRC

Step 1. Calculate the SPD of the index lesions.

Step 2. Identify new, measurable lesions ($\geq 5 \times 5$ mm; up to five new lesions per organ: five new cutaneous lesions and ten visceral lesions).

Step 3. Calculate the SPD of the new, measurable lesions.

Step 4. Calculate the tumor burden:

$$\text{Tumor burden} = \text{SPD}_{\text{index lesions}} + \text{SPD}_{\text{new, measurable lesions}}$$

Step 5. Calculate the change in tumor burden relative to baseline and the change in tumor burden relative to nadir.

Step 6. Derive the overall response using the table below.

Overall Response	Criterion
irCR	Complete disappearance of all lesions (whether measurable or not, and no new lesions) confirmed by a repeat, consecutive assessment ≥ 4 weeks from the date first documented
irPR	Decrease in tumor burden $\geq 50\%$ relative to baseline confirmed by a consecutive assessment ≥ 4 weeks from the date first documented
irSD	Criteria for irCR, irPR, and irPD are not met; does not require confirmation
irPD	Increase in tumor burden $\geq 25\%$ relative to nadir confirmed by a consecutive assessment ≥ 4 weeks from the date first documented

irCR=immune-related complete response; irPD=immune-related progressive disease; irPR=immune-related partial response; irSD=immune-related stable disease.

DETERMINATION OF irBOR

Once a patient has completed all tumor assessments, his/her irBOR may be determined:

Condition	irBOR
At least one irCR	irCR
At least one irPR and no irCR	irPR
At least one irSD and no irCR and no irPR	irSD
At least one irPD and no irCR, no irPR, and no irSD	irPD

irBOR=immune-related best overall response; irCR=immune-related complete response;
irPD=immune-related progressive disease; irPR=immune-related partial response;
irSD=immune-related stable disease.

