3.0 OBJECTIVES

3.1 Primary Objective

1. To determine if this regimen converts patients with resistance to PD-1/PD-L1 checkpoint blockade into responders as determined by abscopal response rate (defined as response rate at lesions not treated with RT + IL-2) using immune related RECIST (irRECIST)
2. To determine the objective response rate (ORR), disease control rate (DCR), and progression free survival (PFS) using RECIST 1.1 (Response Evaluation Criteria for Solid Tumors)

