5.8.1 Discontinuation of Study Therapy Due to Disease Progression

Immunotherapeutic agents such as pembrolizumab and IL-2 may produce antitumor effects by potentiating endogenous cancer-specific immune responses. The response patterns seen with such an approach may extend beyond the typical time course of responses seen with cytotoxic agents and can manifest as a clinical response after an initial increase in tumor burden or even the appearance of new lesions.

Immune related RECIST will be used for assessment of tumor response for the purposes of managing subjects on Protocol treatment and decision making for discontinuation of study therapy due to disease progression. PD should be confirmed no earlier than 4 weeks later according to the criteria outlined in Table 11 below. Subjects who are deemed clinically unstable or who have biopsy proven new metastatic lesions are not required to have repeat imaging for confirmation. This decision will be based on clinical judgment of a subject's overall clinical

condition, including performance status, clinical symptoms, and laboratory data. At a minimum, subjects must meet the following criteria for continued treatment on study after disease progression is identified at a tumor assessment:

When feasible, subjects should not be discontinued until progression is confirmed; however, the decision to continue study treatment after the first evidence of disease progression is at the investigator's discretion based on the clinical status of the subject.

Subjects may receive study treatment while waiting for confirmation of PD if they are clinically stable as defined by the following criteria:

- No decline in ECOG performance status.
- Absence of new or worsening symptoms.
- Absence of rapid progression of disease.
- Absence of progressive tumor at critical anatomical sites (e.g., spinal cord compression) requiring urgent alternative medical intervention.

Table 11. Imaging and Treatment after First Radiologic Evidence of Progressive Disease

	Clinically Stable		Clinically Unstable	
	Imaging	Treatment	Imaging	Treatment
First radiologic evidence of PD	Repeat imaging at \geq 4 weeks to confirm PD	May continue study treatment at the investigator's discretion while awaiting confirmatory scan	Repeat imaging at \geq 4 weeks to confirm PD if possible	Discontinue treatment
Repeat scan confirms PD	No additional imaging required	Discontinue treatment	No additional imaging required	N/A

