7.1.4.3 Evaluation of Best Overall Response

The best overall response is the best response recorded from the start of the treatment until disease progression/recurrence (taking as reference for PD the smallest measurements recorded

since the treatment started). In general, the patient's best response assignment will depend on the achievement of both measurement and confirmation criteria.

Table 12. Best Overall Response Evaluation

Target Lesion	New Lesion	Overall Response
CR	No	CR
PR	No	PR
SD	No	SD
PD	Yes or No	PD

Patients with a global deterioration of health status requiring discontinuation of treatment without objective evidence of disease progression at that time should be classified as having "symptomatic deterioration". Every effort should be made to document the objective progression even after discontinuation of treatment.

In some circumstances it may be difficult to distinguish residual disease from normal tissue.

When the evaluation of complete response depends on this determination, it is recommended that the residual lesion be investigated (fine needle aspirate/biopsy) to confirm the complete response status.

Duration of Overall Response

The duration of overall response is measured from the time measurement criteria are met for CR or PR (whichever status is recorded first) until the first date that recurrence or PD is objectively documented, taking as reference for PD the smallest measurements recorded since the treatment started.

Duration of Stable Disease

SD is measured from the start of the treatment until the criteria for disease progression are met, taking as reference the smallest measurements recorded since the treatment started.

The clinical relevance of the duration of SD varies for different tumor types and grades.

Therefore, it is highly recommended that the protocol specify the minimal time interval required between two measurements for determination of SD. This time interval should take into account the expected clinical benefit that such a status may bring to the population under study.

Disease Control Rate (DCR)

DCR is defined as the percentage of patients that achieve an objective tumor response or stable disease to therapy.

Progression-Free Survival (PFS)

PFS is defined as the duration of time from start of treatment to time of progression or death, whichever occurs first.

Abscopal Response Rate (ARR)

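### Under irRECIST, a patient whose first on-study scan shows progression and who is never rescanned is scored as stable disease and counted as disease control

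*Combined protocol and SAP*

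**What the plan says.** **Response categories.** In Appendix 4, irPD is a rise in tumor burden of at least 25% "relative to nadir confirmed by a consecutive assessment" made 4 weeks or more after the rise was first seen. The entry for irSD is "Criteria for irCR, irPR, and irPD are not met; does not require confirmation". The table of best overall response gives irSD to a patient with "At least one irSD and no irCR and no irPR". Appendix 4 has no category for unconfirmed progression and none for patients who cannot be evaluated.

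**Who is rescanned.** Section 5.8.1 states: "Subjects who are deemed clinically unstable or who have biopsy proven new metastatic lesions are not required to have repeat imaging for confirmation". Table 11 asks for a repeat scan in clinically unstable patients only where it can be done, and has their treatment stopped once progression is first seen on imaging.

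**DCR.** Section 7.1.4.3 states that "DCR is defined as the percentage of patients that achieve an objective tumor response or stable disease to therapy". It names no criteria set there. On stable disease the same section says "it is highly recommended that the protocol specify the minimal time interval required between two measurements for determination of SD", and no interval follows.

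**Which criteria apply to DCR.** The second primary objective in Section 3.1 reads "To determine the objective response rate (ORR), disease control rate (DCR), and progression free survival (PFS) using RECIST 1.1"; Sections 5.2 and 9.1 agree with it. Footnote c of the Study Calendar (Section 6.1) and Table 14 (Section 8.4), where the DCR row is labelled primary, ask for both RECIST and irRECIST. Section 7.1.1 has progression judged by irRECIST.

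**The concern.** Three rules that are each reasonable combine badly. Progression needs a second scan, some progressing patients are excused from that scan, and whatever is not confirmed falls into stable disease. The excused patients are those who deteriorate or whose new metastasis has been proven by biopsy, so they are the least likely to have controlled disease. If they are scored as irSD, the irRECIST DCR is biased upward only, in a population that has already progressed on checkpoint blockade. The irRECIST PFS of the same patients has no rule for dating the progression that was seen.

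**Working it through.** The plan gives no expected DCR, threshold or test, so it has no figure to reproduce. The check applies the stated rules to a patient and then scales the effect.

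**Step 1: classify one patient.** Suppose every lesion grows by 20% in each diameter between baseline and the first on-study scan, and no later scan is made.

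- RECIST (Section 7.1.4.1, Table 12): the sum of longest diameters rises by 20%, which meets the PD threshold. No confirmation is asked for. Result: PD, not disease control.
- Appendix 4: tumor burden is a sum of products of two diameters, so it changes by 1.2 × 1.2 = 1.44, a rise of 44%. This exceeds 25%, but there is no confirming scan, so irPD is not met. Neither is irCR or irPR. Result: irSD, best response irSD, disease control.
- Appendix 4, if a second scan 4 weeks or more later is still at least 25% above nadir: irPD, not disease control.

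The literal Appendix 4 result therefore depends on whether the second scan was made. A biopsy-proven new lesion raises a related question. Appendix 4 takes only index and measurable new lesions into account, so a new lesion too small to measure adds nothing to tumor burden. Under Section 7.1.4.1 any new lesion is PD.

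**Step 2: who is affected.** Only patients whose first on-study scan shows progression and who have no later scan. A patient with an earlier scan showing genuine stable disease has a best response of irSD in any case.

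**Step 3: effect on irRECIST DCR.** Let n = 21 (phase II efficacy set, Section 9.1, assumed here to be the denominator), x = patients with true disease control, and k = patients scored irSD only because no second scan was made.

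Reported DCR = (x + k)/n, so the overstatement is k/n, and 1/21 = 4.8 points per patient.

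Neither x nor k is in the documents. For illustration, assume x = 6:

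| k | (6 + k)/21 | DCR | Exact 95% CI |
|---|---|---|---|
| 0 | 6/21 | 28.6% | 11.3 to 52.2 |
| 1 | 7/21 | 33.3% | 14.6 to 57.0 |
| 2 | 8/21 | 38.1% | 18.1 to 61.6 |
| 3 | 9/21 | 42.9% | 21.8 to 66.0 |
| 4 | 10/21 | 47.6% | 25.7 to 70.2 |

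**Step 4: other endpoints.** RECIST 1.1 DCR and PFS do not change, because the single scan is already PD. Abscopal response does not change, because irSD and irPD are both non-response. For irRECIST PFS, Section 7.1.4.3 counts progression or death. With irPD unmet at the scan, the event waits for later documentation or death.

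**The case against.** The strongest reply is that the primary DCR is defined by RECIST 1.1 in Sections 3.1, 5.2 and 9.1, and is sound. That stands. A reader might infer that the primary DCR as a whole is inflated; the documents do not support this. The irRECIST version nevertheless cannot be set aside, because Table 14 labels DCR primary under both criteria, Section 7.1.1 has progression judged by irRECIST, and no text says which version governs.

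Second, Section 5.8.1 can be read as waiving confirmation, so that the progression seen on the single scan stands. That is a fair reading. Appendix 4 contains no matching exception, however, so the two texts are unreconciled.

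Third, the reporting rules in Section 7.1.4.3 count progression, early death and not-assessable patients as failures. Those rules concern the response rate, leave the exact definitions to be supplied, and do not say whether this patient is stable, progressed or not assessable. They show that the literal result is not the only one possible, but they do not settle it.

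Fourth, a reader might infer that every unconfirmed progression becomes disease control. That goes too far. Table 11 asks for repeat imaging in stable patients, and where a repeat scan refutes progression, a non-PD category is what irRECIST intends.

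Fifth, it is tempting to say that the irRECIST PFS event disappears. It does not: death counts, and Section 5.11 continues follow-up every 3 months.

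Finally, the missing minimum for stable disease is only a missing detail. Scans every 3 cycles of 3 weeks put the first one at about 3 × 3 = 9 weeks (Section 8.1 says 6), which acts as an informal floor.

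**Conclusion.** The point holds for irRECIST DCR and irRECIST PFS. On a literal reading of Appendix 4, a patient who progresses at the first on-study scan and is not rescanned counts as disease control. Each adds 4.8 points with 21 patients in the denominator. The number of such patients is unknown, so the total overstatement cannot be stated; the table above is illustration only. The irRECIST PFS event is left undated until later documentation or death.

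No decision rule uses DCR, and Section 9.4 calls all results preliminary. The correction is still worth making before analysis, because in a small open-label trial the classification of a few patients should not be left to choice after the data are seen.

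**What to change.** In Section 7.1.4.3 and Appendix 4:

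1. Add a category for unconfirmed irPD with no later scan. Score it as PD (not disease control) for irRECIST DCR, and date the irRECIST PFS event at that scan.
2. State that patients whose repeat scan refutes progression keep their irSD, irPR or irCR. A rule that required a progression-free first scan would wrongly exclude them.
3. Reconcile Section 5.8.1, the reporting categories in Section 7.1.4.3 and Appendix 4, including how a biopsy-proven new lesion is scored.
4. State whether RECIST 1.1 or irRECIST defines the primary DCR, and make Sections 3.1, 5.2, 6.1, 7.1.1, 8.4 and 9.1 agree.

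This changes scoring only, not who is scanned or treated. It costs a few sentences. The irRECIST DCR becomes slightly less favourable, and a patient with pseudoprogression who was never rescanned would be scored as progressed.
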